9.2. Sample Size Determination

The number of participants chosen is to provide sufficient power for the non-inferiority comparisons stated in Section 9.1.

The following assumptions were made in the sample size determinations:

- Log transformed (log10 scale) immune response data are normally distributed
- A common standard deviation (SD): SD 0.5 (log10 scale) of the immune response log transformed data
- Non-inferiority margin $\log_{10}(2/3) = -0.176$

- Alpha 0.025 (one-sided). Using a Bonferroni correction, Type I error will be split equally over the 1-dose and 2-dose comparisons: 0.0125 (1-sided) for 1- and 2-dose NI comparisons
- Power 90%

Based on the above assumptions, assuming approximately a 10.2% dropout, a sample size of 225 participants per active vaccine group (see [Table 1](#)) is needed to detect non-inferiority of testing 1-dose and 2-doses of 9×10^{10} vp, 2.5×10^{10} vp, 7×10^{10} vp, 3.5×10^{10} vp, and 1.25×10^{10} vp Ad26.COV2.S as the test groups versus 1-dose and 2-doses of 5×10^{10} vp Ad26.COV2.S (release titer) as the reference groups, with 90% power.

A target of approximately 240 participants (40 seronegative and 20 seropositive participants) per dose regimen in Groups 1, 3, 5, and 6 will be enrolled to further characterize the innate, pro-inflammatory and other relevant (eg, pro-thrombotic) responses to Ad26.COV2.S to better understand a possible risk to TTS events. This target may not be met due to the challenges of enrolling seronegative subjects into the study, so sub-study enrollment may stop at lower numbers.

Participants in the main study and sub-study (participants who are seronegative at enrollment or baseline) may be combined for the analysis.

[Table 7](#) shows how the power will be affected with 10%, 20%, 30%, 40%, 50% and 60% dropout due to various reasons (eg, lost to follow-up, participants with major protocol deviations with impact on immunogenicity, participants who become N-seropositive during the study or with a confirmed SARS-CoV-2 infection, and participants who received their vaccination outside the allowed window).

Table 7: Power Based on % of Drop Out

Regimen	sample size at enrollment per arm	group	% drop out since enrollment					
			10%	20%	30%	40%	50%	60%
9×10^{10} vp (sample size of main study and sub-study)	252 (212+40)	1	92.00%	88.60%	83.70%	76.80%	68.10%	57.20%
2.5×10^{10} vp (sample size of main study and sub-study)	252 (212+40)	5	92.00%	88.60%	83.70%	76.80%	68.10%	57.20%

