1.3. Study Design

Main Study

This is a randomized, double-blind Phase 3 study to evaluate 6 dose levels of Ad26.COVID2.S administered as a 2-dose schedule in healthy adults. In this main study, the safety, reactogenicity, and immunogenicity of 1 dose (dose 1 of the 2-dose regimen) and 2-doses of Ad26.COVID2.S will be evaluated. The lower dose (3.5×10^{10} vp, 2.5×10^{10} vp, and 1.25×10^{10} vp) levels mimic vaccine degradation to enable determination of product expiry. In order to increase the end of shelf-life specifications a potential target release titer of 7×10^{10} vp will be evaluated. A higher titer of 9×10^{10} vp will also be evaluated as is the upper limit of the release range (potential maximum vp at release). The study population will consist of healthy men and women aged between 18 and 55 years (inclusive), who have not previously received a vaccine against COVID-19 and have not had prior exposure to SARS-CoV-2 as assessed by local serology testing. Participants will receive Ad26.COVID2.S administered IM.

The study duration from screening until the last follow-up visit will be at least 8 months per participant. The study will consist of a 28-day screening phase with vaccinations on Day 1 and Day 57, and a follow-up of at least 6 months after the last vaccination.

A target of approximately, 1,350 participants (225 participants per active vaccine group) in the main study will be randomized in parallel in a 1:1:1:1:1:1 ratio to 1 of 6 vaccination groups in this study. Participants will receive a 2-dose vaccination regimen at different dose levels (9×10^{10} vp, 2.5×10^{10} vp, 7×10^{10} vp, 5×10^{10} vp, 3.5×10^{10} vp, and 1.25×10^{10} vp).

Table 2: Schematic Overview of Main Study Design and Groups

Group	N	Day 1 Vaccination 1	Day 57 Vaccination 2
1	For NI ~ 225	Ad26.COV2.S 9×10^{10} vp	Ad26.COV2.S 9×10^{10} vp
2	For NI ~ 225	Ad26.COV2.S 7×10^{10} vp	Ad26.COV2.S 7×10^{10} vp
3	For NI ~ 225	Ad26.COV2.S 5×10^{10} vp	Ad26.COV2.S 5×10^{10} vp
4	For NI ~ 225	Ad26.COV2.S 3.5×10^{10} vp	Ad26.COV2.S 3.5×10^{10} vp
5	For NI ~ 225	Ad26.COV2.S 2.5×10^{10} vp	Ad26.COV2.S 2.5×10^{10} vp
6	For NI ~ 225	Ad26.COV2.S 1.25×10^{10} vp	Ad26.COV2.S 1.25×10^{10} vp

Sub Study

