3. SAMPLE SIZE DETERMINATION

The number of participants chosen is to provide sufficient power for the non-inferiority comparisons.

The following assumptions were made in the sample size determinations:

Log transformed (\log_{10} scale) immune response data are normally distributed

A common standard deviation (SD): SD=0.5 (\log_{10} scale) of the immune response log transformed data

Non-inferiority margin = $\log_{10}(2/3) = -0.176$

Alpha = 0.0125 (1-sided) for 1- and 2-dose NI comparisons

- Alpha = 0.025 (one-sided). Using a Bonferroni correction, Type I error will be split equally over the 1-dose and 2-dose comparisons: 0.0125 (1-sided) for 1- and 2-dose NI comparisons

Power = 90%

Based on the above assumptions, and approximately a 10% dropout, a sample size of 225 participants per active vaccine group (see [Table 2](#)) is needed to detect non-inferiority of testing 1-dose and 2-doses of 9×10^{10} vp, 2.5×10^{10} vp, 7×10^{10} vp, 3.5×10^{10} vp, and 1.25×10^{10} vp Ad26.COV2.S as the test groups versus 1-dose and 2-doses of 5×10^{10} vp Ad26.COV2.S (release titer) as the reference groups, with 90% power (main study sample size assessment).

The originally intended NI population was comprised of participants from the main study who were SARS-CoV-2 seronegative at baseline and non-previously vaccinated. In addition, participants becoming infected with SARS-CoV-2 during the study are excluded from this population from the time of infection.

Participants were screened using a local SARS-CoV-2 serology test to ensure only participants who were seronegative at baseline were enrolled in the main study. However, a preliminary blinded evaluation of central N-serology results in main study participants at Day 29 and Day 71 showed that overall, 27% and 38% of participants, respectively, were N-serology positive at these time points. The higher-than-expected N-serology positive status at Day 29 and Day 71 indicated that participants became infected during the study and/or local serology tests were not sufficiently sensitive, affecting the power of the study.

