For the sub-study (initiated to further characterize the innate, pro-inflammatory and other relevant (e.g., prothrombotic) responses to Ad26.COV2.S to better understand a possible risk to TTS events), a target of approximately 240 participants will be enrolled and will receive a 2-dose vaccination regimen at either 9×10^{10} vp, 2.5×10^{10} vp, 5×10^{10} vp, or 1.25×10^{10} vp. As participants in the sub-study share common blood sampling timepoints with the main study, data from both cohorts can be merged for analyses. Due to the higher-than-expected N serology positive results in the main study affecting the power of the study, the non-inferiority assessment will combine participants from the main study and sub-study.

Table 4 below shows how, when combining main and sub study participants (randomized as SARS-CoV-2 seronegative at baseline based on local serology by finger prick testing), the power is affected due to a hypothetical 10%, 20%, 30%, 40%, 50% and 60% loss of evaluable participants (lost due to various reasons, e.g. lost to follow-up, participants with major protocol deviations with impact on immunogenicity, participants who become infected with SARS-CoV-2, participants who received their vaccination outside the allowed window, etc.).

Table 4: Impact of loss of evaluable subjects on NI assessment power

Dose level	Sample size at enrollment per arm (main study + sub study)	Group	% loss of evaluable participants since enrollment					
			10%	20%	30%	40%	50%	60%
9x1010 vp	265(225+40)	1	94%	91%	87%	81%	73%	62%
2.5x1010 vp	265(225+40)	5	94%	91%	87%	81%	73%	62%
7x1010 vp	225 (225+0)	2	90%	86	81%	74%	65%	54%
5x1010 vp	265(225+40)	3	94%	91%	87%	81%	73%	62%
3.5x1010 vp	225 (225+0)	4	90%	86	81%	74%	65%	54%
1.25x1010 vp	265(225+40)	6	94%	91%	87%	81%	73%	62%

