4.2. Selection of NI dataset

Decision for selection of population for non-inferiority testing

Participants were screened using a local SARS-CoV-2 serology test to ensure that only participants who were seronegative at baseline were enrolled in the main study (or randomized as seropositive

or seronegative at baseline in the sub study). Prior to Primary Analysis, a preliminary blinded evaluation of central N-serology results in main study participants at Day 29 and Day 71 showed that overall, 27% and 38% of participants, respectively, were N-serology positive at these time points. The higher-than-expected N-serology positive status at Day 29 and Day 71 indicated that participants became infected during the study and/or local serology tests were not sufficiently sensitive, affecting the power of the study.

While data following SARS-CoV-2 infections during the study will be excluded from non-inferiority assessments, data from participants who are seropositive at baseline as assessed by central testing could be included in the non-inferiority assessment if serostatus at baseline is considered as an independent variable (scenario 2).

Based on these considerations, only one of two scenarios will be considered for primary analysis. If there is an overall loss of > 40% evaluable data points in the NI set at Day 29 (defined as number of evaluable participants in the NI set at D29/total number of subjects in Table 4), the population in scenario 2 will be used for primary analysis.

Scenario 1 (base case scenario): non-inferiority will be performed on the NI set including participants from the main study and sub-study.

Scenario 2: Non-inferiority analysis will be performed on the PPI set including participants from the main study and sub-study. In this scenario a model accounting for SARS-CoV-2 serostatus at baseline will be used.

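### SAP Table 4 and protocol Table 7 disagree on enrolment per arm (totals 1,510 and 1,432), and the SAP's >40% loss rule for choosing the primary NI population divides by the Table 4 total

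*SAP*

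**What the plan says.** Both documents plan the main study at 225 per arm. SAP Section 3 asks for "a sample size of 225 participants per active vaccine group" to give 90% power with about 10% dropout, and protocol Sections 4.1 and 9.2 give the same target with 10.2% dropout. SAP Section 1 states that it is based on protocol amendment 7.

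Each document then tabulates power against loss of participants. Protocol Table 7 labels its size column "sample size at enrollment per arm"; SAP Table 4 labels its own "Sample size at enrollment per arm (main study + sub study". The entries are:

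| | 9, 5, 2.5 and 1.25x10^10 vp | 7 and 3.5x10^10 vp | Power at 40% loss |
|---|---|---|---|
| Protocol Table 7 | 252 (212+40) | 212 | 76.8% / 72.7% |
| SAP Table 4 | 265 (225+40) | 225 | 81% / 74% |

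SAP Section 4.2, repeated in Section 5.5.3.1, uses Table 4 to choose the primary NI population. If overall loss at Day 29 exceeds 40%, the analysis moves from Scenario 1 (NI set, dose level only) to Scenario 2 (PPI set, with baseline serostatus in the model). The loss is "defined as number of evaluable participants in the NI set at D29/total number of subjects in Table 4". Protocol Section 9.4.2 has a different criterion: baseline-seropositive participants are included if power for the combined main study and sub-study falls below 80%. Protocol Section 9.2 also lets the sub-study stop short of its 40 seronegative participants per arm.

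**The concern.** Two tables under the same label cannot both describe enrolment. The SAP's 225 is the recruitment target. The protocol's 212 is unexplained, and it is not the target less dropout either, since 225 x (1 - 0.102) = 202.

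The difference matters because the SAP total is the fixed denominator of a decision rule. If fewer people entered than Table 4 assumes, the shortfall is booked as loss before anyone drops out, and Scenario 2 starts earlier than its 40% label suggests. Crossing the cut changes both the population (baseline seropositives come in) and the model for every primary comparison.

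The region near the cut is plausible. SAP Section 3 reports 27% N-positive at Day 29 in a blinded look at the main study. As an illustration only, adding the planned 10.2% dropout gives 1 - 0.73 x 0.898 = 34% or, if simply summed, 37%. Exclusions for central baseline seropositivity or missing baseline serostatus could add to this, although they may overlap with the 27%.

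**Working it through.** **Inputs.** SAP Section 3 gives "Alpha = 0.0125 (1-sided) for 1- and 2-dose NI comparisons", a common SD of 0.5 on the log10 scale, and a margin of log10(2/3), that is 0.1761 in size. A true GMC ratio of 1 is my assumption; neither document states it. Sizes are those of the two tables.

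**Formula.** For evaluable numbers n1 and n2, df = n1 + n2 - 2 and noncentrality = 0.1761 / (0.5 x sqrt(1/n1 + 1/n2)). Power is the probability that a noncentral t with these parameters exceeds the 0.9875 quantile of the central t.

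**1. Reproducing SAP Table 4** (10% to 60% loss):
- 265 v 265: 94.5, 91.5, 87.3, 81.2, 73.0, 62.1%. Stated: 94, 91, 87, 81, 73, 62%.
- 225 v 225: 90.2, 86.2, 80.8, 73.8, 65.0, 54.2%. Stated: 90, 86, 81, 74, 65, 54%.

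Every cell agrees within 1 point. Against the pooled 5x10^10 vp arm (225 v 265), the main-only doses reach 77.5% at 40% loss, so the stated 74% is conservative.

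**2. Reproducing protocol Table 7:**
- 252 v 252: 93.3, 90.0, 85.4, 79.0, 70.5, 59.6%. Stated: 92.0, 88.6, 83.7, 76.8, 68.1, 57.2%.
- 212 v 212: 88.2, 83.9, 78.2, 71.0, 62.1, 51.4%. 212 v 252: 90.9, 87.0, 81.8, 74.9, 66.1, 55.3%. Stated: 89.4, 85.0, 79.9, 72.7, 63.7, 53.0%.

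Neither row matches its own n. The first reproduces within 0.3 points at 240 per arm (76.8% at 40% loss), the second at 220 per arm (72.8%).

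**3. The denominator.** 4 x 265 + 2 x 225 = 1,510. 4 x 252 + 2 x 212 = 1,432. The difference is 78, and 78/1,510 = 5.2%.

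**4. The trigger if 1,432 were enrolled.** The rule fires below 0.6 x 1,510 = 906 evaluable.
- True loss at that point: 1 - 906/1,432 = 36.7%.
- A true 40% loss leaves 0.6 x 1,432 = 859 evaluable and reads as 1 - 859/1,510 = 43.1%.

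**5. Sub-study shortfall** (assumed range of 0 to 40 seronegatives per arm, 212 in the main study). Enrolment runs from 6 x 212 = 1,272 to 1,432. The number counted as lost without having entered runs from 238 down to 78, and the rule fires at a true loss of 1 - 906/1,272 = 28.8% up to 36.7%.

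**6. Power at the trigger as written.** With 1,432 enrolled and losses even across arms, 906 evaluable is 252 x 906/1,432 = 159.4 and 212 x 906/1,432 = 134.1 per arm. Power is 81.3% for the pooled doses. For 7 and 3.5x10^10 vp it is 73.5% with equal arms, or 77.4% against the pooled reference. SAP Table 4 states 81% and 74%.

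**7. Power if only the denominator changed to 1,432.** The trigger moves to 859 evaluable, about 151 and 127 per arm. Power is 79.0% for the pooled doses and 71.0% with equal main-only arms (74.9% against the pooled reference).

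**The case against.** A reader might infer that the SAP overstates power at the trigger, because its 81% belongs to a larger trial. The documents do not support that. Power depends on the evaluable count, and dividing by 1,510 pins that count at 906 however many entered. Step 6 shows that the stated 81%/74% then holds. The two feared consequences exclude each other: with 1,510 as denominator, people who never entered may be counted as lost but power at the switch is as stated; with 1,432, nobody is wrongly counted but power at the switch is 79.0% for the pooled doses. Even at a true 40% loss, the 7 and 3.5x10^10 vp doses (212 v 252) have 74.9%, which is not below the stated 74%.

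A reader might also take 212+40 as actual enrolment. Neither document says so. Both keep the 225 and 1,350 targets elsewhere, and the 40 is itself a target. The 78 and the 36.7% are therefore conditional.

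It can fairly be added that, with a full sub-study, the affected band is only 40 - 36.7 = 3.3 points wide, that the rule uses an overall count rather than treatment outcomes, and that a fixed evaluable count protects power better than a denominator of actual enrolment. All of this stands. It does not remove the unexplained conflict between the tables, or the fact that the percentage in the rule does not mean what it says unless Table 4 equals actual enrolment.

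**Conclusion.** The two documents give different enrolment per arm, and the SAP's choice of primary NI population rests on the version built from planning targets. If the protocol's figures are true, Scenario 2 starts at 36.7% true loss rather than 40%, and as early as 28.8% if the sub-study contributed no seronegatives. Power at the trigger as written is not overstated, given even losses across arms, SD 0.5 and a true ratio of 1.

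Two further points stand without any assumption about enrolment. Under the stated design inputs and a true ratio of 1, protocol Table 7's powers do not follow from its own sample sizes. And the bracket in SAP Sections 4.2 and 5.5.3.1 defines loss as evaluable over total, which is the fraction retained. Read literally, it would select Scenario 2 whenever more than 0.4 x 1,510 = 604 participants were evaluable, the reverse of what is meant.

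**What to change.** 1. Replace the sizes in SAP Table 4 and protocol Table 7 with the numbers actually randomised as locally seronegative in each arm (main study plus sub-study), and recompute both sets of powers at those numbers. State the assumed true ratio and whether the 7 and 3.5x10^10 vp rows are compared with the pooled reference arm.
2. State the Scenario 2 trigger as an evaluable count at Day 29 tied to the 80% power criterion in protocol Section 9.4.2. Alternatively, keep a percentage of the actual randomised total, but re-derive the cut so that it still meets that criterion. Changing the denominator alone is not enough: at 1,432 the pooled doses would already be at 79.0% when the rule fires.
3. Say which comparison the 80% refers to. From the protocol's sizes, 80% is reached at 38.7% loss for 252 v 252 but at 32.9% for 212 v 252.
4. Define loss as 1 minus evaluable/total in both SAP sections.

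The cost is a recalculation of the power table at one agreed set of counts, carried into both documents, and one rule restated. No new data are needed. The restated cut should be fixed before the Day 29 evaluable count is known.

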4. POPULATIONS (ANALYSIS SETS) FOR ANALYSIS

For vaccine studies, study intervention assignment will follow the as treated principle: all analyses (including safety, immunogenicity) will be analyzed by the received vaccine.

Analysis Sets	Description
All screened participants (ALL)	The “all screened participants” set includes all participants that were screened, regardless of whether they were enrolled and/or randomized.
All randomized participants (ALL RANDOMIZED)	The “all randomized participants” set includes all participants that were randomized to one of the treatment groups.
Full Analyses Set (FAS)	The Full Analysis Set will include all participants with at least one vaccine administration documented
Per Protocol Immunogenicity Set (PPI)	The Per Protocol Immunogenicity population will include all randomized and vaccinated participants for whom immunogenicity data are available excluding participants with major protocol deviations expected to impact the immunogenicity outcomes (see section 4.1). In addition, samples obtained after missed vaccinations or samples obtained from participants after SARS-CoV-2 infection occurring after screening (if applicable) will be excluded from the analysis set (see below section 4.1).
NI Analysis Set	The NI analysis set will include all PPI participants who are SARS-CoV-2 seronegative at study entry ^a .

^a SARS-CoV-2 seronegative as assessed by central testing (based on S- and/or N- serology at baseline)

NB. As detailed in Section 4, formal non-inferiority hypothesis testing will be performed on either the NI set or on the PPI set under different scenarios (Scenario 1 or Scenario 2, respectively).

Further details on the selection of PPI and NI set are described below.

The safety and reactogenicity analyses will be censored at the date of unblinding or the receipt of an unscheduled vaccine, whichever event occurs first. AEs reported after unblinding or receipt of an unscheduled vaccine, whichever comes first, will be listed.

The immunogenicity analyses will be censored at the date of the receipt of an unscheduled vaccine. Immunogenicity samples taken after the receipt of an unscheduled vaccine will be included in the listings and flagged.

If a participant is vaccinated out of window (see section 1.4.1 of the protocol) due to a study pause (see section 6.9 of the protocol), this will not by default be a reason for excluding this participant from the PPI. The list of major protocol deviations to be excluded from the immunogenicity analyses will be specified in the major protocol deviation criteria document and/or this list will be reported into the protocol deviation dataset of the clinical database before database lock.

4.1. Selection of PPI dataset

- Samples obtained from participants after SARS-CoV-2 infection occurring after screening (if applicable) will be excluded from the analysis set.
 - This includes COVID-19 cases with a positive RT-PCR or molecular test, but also participants who develop a post-baseline positive result in non-S-based serology (e.g. N-ELISA or equivalent assay, such as the Roche Elecsys anti-SARS-CoV-2 assay) if the test was negative at baseline. Samples at the time of positive RT-PCR or molecular test, or non-S-based serology and thereafter will be excluded from PPI.
 - Participants with missing or having undetermined SARS-CoV-2 serostatus at baseline will be excluded from PPI.
- Major Protocol Deviations (MPDs) with impact on immunogenicity will be considered for the PPI population. MPDs are defined in the MPD Criteria document. Different rules are applicable for selected MPDs with impact on immunogenicity:
 - For MPDs with impact on immunogenicity which concern inclusion or exclusion criteria (category: entered but did not satisfy criteria), the whole subject will be excluded from PPI.
 - For MPDs with impact on immunogenicity which can affect immunogenicity outcomes from the time of PD and thereafter, such as missed vaccinations, out of window vaccinations (Day 57 visit), use of disallowed concomitant medications or off-study COVID-19 vaccines (categories: received a disallowed concomitant treatment, received wrong treatment or incorrect dose, developed withdrawal criteria but no withdrawn, in addition to ‘missed vaccination’ under the category ‘Other’, and ‘received vaccination outside of visit window’ under the category ‘Dosage & Administration’), any samples obtained at the time of PD and thereafter will be excluded from PPI. Samples taken from the subject prior to such PDs can be included in PPI.
 - For MPDs with impact on immunogenicity which can affect immunogenicity outcomes only at the time of PD, such as out of window visits or blood collections (category: Other except for missed vaccination or out of window vaccinations which is included in the rule above), samples obtained at the time of PD will be excluded from PPI only. Samples taken from the subject prior to or after such PDs can be included in PPI.
 - The exact PD rules may be amended, or other PD types may be added, this will be further described in the DPS. For PDs relating to out of window visits or sampling, the windows will be defined as indicated in Section 5.1.3.

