- e. For those participants who are unable to continue participation in the study up to Visit 7, but for whom consent is not withdrawn, an early exit visit will be conducted as soon as possible. Participants who wish to withdraw consent from participation in the study will be offered an optional visit for safety follow-up. This includes the safety assessments of the early exit visit (no blood sampling for immunogenicity). If the participant does not want to receive the second vaccination, they can continue with other study procedures.
- f. Signing of the ICF should be done before any study-related activity.
- g. A history-directed physical examination, including height and body weight, will be carried out at screening. At other visits, an abbreviated, symptom-directed examination will be performed if determined necessary by the investigator.
- h. Heart rate, systolic and diastolic blood pressure, respiratory rate, and body temperature. Heart rate and blood pressure measurements should be taken in the supine position and preceded by at least 5 minutes of rest. Vital signs measurements are recommended before blood sampling. Body temperatures will be measured preferably via the oral route.
- i. The blood draw at screening will be used to determine serostatus by serological testing for eligibility in the main and sub study by a local laboratory.
- j. Investigator must check for acute illness or body temperature $\geq 38.0^{\circ}\text{C}/100.4^{\circ}\text{F}$ at the time of vaccination. If any of these events occur within 24 hours prior to planned vaccination, the vaccination can be rescheduled as long as this is in agreement with the allowed windows. If the vaccination visit cannot be rescheduled within the allowed window or the contraindications to vaccination persist, the sponsor should be contacted for further guidance. The investigator should also check if any other reasons, as listed in Section 7.1, Discontinuation of Study Vaccination, have been met and would prevent further study vaccination.
- k. For women of childbearing potential only.
- l. Serum collected can also be used for N-serology testing.

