A target of approximately 240 participants will be enrolled in the sub study and will receive a 2-dose vaccination regimen at either 9×10^{10} vp, 5×10^{10} vp, 2.5×10^{10} vp, or 1.25×10^{10} vp. This target may not be met due to the challenges of enrolling seronegative subjects into the study, so sub-study enrollment may stop at lower numbers.

Table 2: Schematic Overview of Study Design and Groups for the Sub Study

Group	N (Seronegative)*	N (Seropositive)	Day 1 Vaccination 1	Day 57 Vaccination 2
1	~ 40	~ 20	Ad26.COV2.S 9×10^{10} vp	Ad26.COV2.S 9×10^{10} vp
3	~ 40	~ 20	Ad26.COV2.S 5×10^{10} vp	Ad26.COV2.S 5×10^{10} vp
5	~ 40	~ 20	Ad26.COV2.S 2.5×10^{10} vp	Ad26.COV2.S 2.5×10^{10} vp
6	~ 40	~ 20	Ad26.COV2.S 1.25×10^{10} vp	Ad26.COV2.S 1.25×10^{10} vp

*Due to the challenges of enrolling seronegative subjects into the study, study enrollment may stop at lower numbers.

Table 3: Humoral Immunity Blood Sampling Schedule in Participants in All Groups of the Main and Sub Study

Groups**		Month 1	Month 2	Month 3	Month 6*	
	Day 1	Day 29	Day 57	Day 71		
1 6	●	●	●	●	●	

*post last vaccination

**Groups 1, 3, 5 and 6 in the sub study

Table 4: SARS-CoV-2 Non-S Serology Schedule in Participants in All Groups of the Main and Sub Study

Groups**		Month 1	Month 2	Month 3	Month 6*	
	Day 1	Day 29	Day 57	Day 71		
1 6		●		●		

*post last vaccination

** Groups 1, 3, 5 and 6 in the sub study

Table 5: Serum Sampling and PaxGene Schedule for Innate MoA in Participants in Groups 1, 3, 5 and 6 of the Sub Study

Groups	Day 1*	Day 2	Day 4	Day 8	Day 57*	Day 58	Day 60	Day 64
1, 3, 5 and 6	●	●	●	●	●	●	●	●

*pre vaccination

MoA=mechanism of Action

An IDMC has been commissioned for the Ad26.COV2.S program. Any significant safety information will be shared with the IDMC. Refer to Committees Structure in Section 10.3, for details.

A diagram of the study design is provided in Section 1.2, Schema.

Study Duration

The study duration from screening until the last follow-up visit will be at least 8 months per participant. The study will consist of a 28-day screening phase with vaccinations on Day 1 and Day 57, and a follow-up of at least 6 months after the last vaccination.

The vaccination phase consists of the administration of 1-dose of Ad26.COV2.S on Day 1 and 1-dose of Ad26.COV2.S on Day 57. A follow-up of at least 6 months after vaccination 2, is foreseen.

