Serologic conversion between baseline (Day 1; pre-vaccination) and selected timepoints post-vaccination using an ELISA and/or SARS-CoV-2 immunoglobulin assay that is dependent on the SARS-CoV-2 N protein (e.g., N-ELISA or equivalent assay, such as the Roche Elecsys anti-SARS-CoV-2 assay), for participants that are N serology negative at baseline.

The proportion of participants who serologically converted will be graphically visualized and tabulated at every available timepoint by randomized group, together with the numbers of participants with an available measurement.

The number of participants with missing baseline N serology results will also be summarized.

Additional tabulation will summarize the number of participants with and without a SARS-CoV-2 infection as having:

Not infected

Asymptomatic or undetected participants

Antibodies binding to the SARS-CoV-2 nucleocapsid (N) protein

For antibodies binding to the SARS-CoV-2 nucleocapsid (N) protein, the number and percentage of participants with a positive sample at Day 1, Day 29, Day 71, Week 32 and Week 60 (if applicable) will be tabulated. A positive or negative result will be obtained from the assay (qualitative assay).

In contrast to the other immunogenicity analyses, this analysis will be performed only on the FAS.

The definition of the PPI analysis set incorporates the N-serology sample positivity assessment: immunogenicity samples obtained after a positive N-serology result post baseline will be excluded from the PPI analysis if the baseline N serology result was negative, as this is indicative of a SARS-CoV-2 infection during the study.

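### Day 57 samples can stay in the per-protocol immunogenicity set after an undetected infection, because N-serology is not planned at Day 57 and the exclusion rule starts only at the positive test

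*SAP*

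**What the plan says.** SAP 4.1 states the aim in terms of infection: "Samples obtained from participants after SARS-CoV-2 infection occurring after screening (if applicable) will be excluded from the analysis set". Protocol 9.3 and 9.4.1 put it the same way. The sentence that puts this into practice is in terms of the test: "Samples at the time of positive RT-PCR or molecular test, or non-S-based serology and thereafter will be excluded from PPI". SAP 6.1.4 repeats it: "immunogenicity samples obtained after a positive N-serology result post baseline will be excluded from the PPI analysis if the baseline N serology result was negative". Neither section looks back to samples drawn before the first positive result.

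Humoral serum is drawn at Days 1, 29, 57, 71 and Month 6 (Protocol 4.1, Table 3). N-serology has a sparser schedule. Protocol Table 4, titled "SARS-CoV-2 Non-S Serology Schedule in Participants in All Groups of the Main and Sub Study", marks Days 29 and 71. Protocol Appendix 2 lists no test before vaccination 2. SAP 6.1.4 tabulates "the number and percentage of participants with a positive sample at Day 1, Day 29, Day 71, Week 32 and Week 60". Day 57 is thus the only scheduled humoral visit without a planned N-result. Footnote l of the schedules of activities (Protocol 1.4.1 and 1.4.2) leaves the option open: "Serum collected can also be used for N-serology testing".

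On how common infection was, SAP 3 and 4.2 report from a preliminary blinded look at main-study participants at Days 29 and 71 that "27% and 38% of participants, respectively, were N-serology positive at these time points".

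**The concern.** A participant who is N-negative at Day 29 and N-positive at Day 71 seroconverted somewhere in those 42 nominal days, and 28 of them come before Day 57. The rule drops the Day 71 sample and keeps the Day 57 sample, although that sample may already be post-infection.

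A positive PCR would close the gap, but it is an incomplete backstop. Study swabs are scheduled only at screening and Day 1; later positives reach the database through off-study tests that participants report. Asymptomatic infection, which N-serology is there to find, is easily missed that way.

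Day 57 is the last measurement after a single dose before dose 2. The secondary objective covers response and durability at every blood collection time point, and SAP 5.6.3 summarises S-ELISA at all of them. Titres raised by infection push up the Day 57 GMC and the fold rise from baseline, and can hide waning after dose 1 in the set that is presented as free of post-infection samples.

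**Working it through.** The documents give no figure for the share of Day 57 samples drawn after infection, so there is no stated value to reproduce. The estimate below uses their inputs.

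**Inputs.** N-positive 27% at Day 29 and 38% at Day 71 (SAP 3 and 4.2); nominal visit days 29, 57 and 71 (Protocol 1.4).

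**Converters between Day 29 and Day 71.** 38% − 27% = 11 points of all participants. Among those N-negative at Day 29: 11/73 = 15.1%.

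**Share by Day 57, even spread (assumption).** (57 − 29)/(71 − 29) = 28/42 = 0.667, so 11 × 0.667 = 7.3 points of all participants.

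**Share of Day 57 PPI samples.** The denominator depends on how many of the 27% were already positive at baseline. The infection rule applies only to participants who were N-negative at baseline, so baseline positives remain in the PPI.
- None of the 27% positive at baseline: 7.3/73 = 10.0% (constant hazard instead of even spread: 10.3%).
- Half of them: 7.3/86.5 = 8.5%.
- All of them: 7.3/100 = 7.3%.

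**Further assumptions, applied to the 10.0%.**
- If a quarter to a half of these infections were known by PCR before Day 57, they are already excluded: 10.0% × 0.75 = 7.5%; 10.0% × 0.5 = 5.0%.
- If N-antibody appears L days after infection, the share infected before Day 57 is (28 + L)/42. L = 7 gives 0.833 × 15.1% = 12.6%; L = 14 gives 1.0 × 15.1% = 15.1%.

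That yields roughly 5% to 15%. It is indicative, not a bound: combining the lowest denominator case with half PCR-known gives 7.3% × 0.5 = 3.7%.

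**Inflation of the Day 57 GMC.** If a fraction f of samples is raised k-fold, the geometric mean is multiplied by k^f. The fold rise k is assumed; the documents give none.

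| f | k = 3 | k = 5 | k = 10 |
|---|---|---|---|
| 5% | 1.06 | 1.08 | 1.12 |
| 7.3% | 1.08 | 1.12 | 1.18 |
| 10% | 1.12 | 1.17 | 1.26 |
| 15% | 1.18 | 1.27 | 1.41 |

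**The case against.** The strongest reply is that the consequence is small and the size uncertain. Most of it stands.

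- **The prevalence figures are weak.** They are preliminary, cross-sectional and from the main study only, and the SAP itself says part of the 27% may be baseline positives that the local test missed. The PPI also takes in sub-study participants, including a target of about 80 seropositives (4 groups × 20). A reader might take 10% as an established contamination rate; the documents support only a range that depends on assumptions.
- **The primary analysis is untouched.** A reader might infer that the non-inferiority conclusions are at risk. They are not: the tests use Days 29 and 71, and the Day 71 samples of these participants are excluded. For the same reason the PPI fold rise from pre-dose 2 to Day 71 is unaffected.
- **Dose comparisons are hardly blurred.** Even if infection made titres identical across arms, 10% contamination would move a true GMC ratio of 2/3 only to (2/3)^0.9 = 0.69, and no Day 57 dose test is planned.
- **Responder rates have little room to move.** For a participant at or below the LLOQ at baseline, any later value above it counts as a response (SAP 6.1.4). The Protocol introduction reports antibody responses in almost all participants after one dose of other Ad26 vaccines.
- **Some safeguards exist.** FAS analyses show participants infected during the study as a subgroup. That helps interpretation but does not correct the PPI summary.

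There is also a fair objection to excluding every such Day 57 sample as the main rule. It selects on a later result, and under even spread 14/42, a third, of the samples dropped would be pre-infection. If low responders are infected more often (an assumption), dropping them would itself raise the GMC.

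**Conclusion.** The gap is real. The stated aim is to exclude samples taken after infection; the operating rule excludes from the positive result onward; and Day 57 has no planned N-result. Participants who are N-negative at Day 29, first N-positive at Day 71 and without a reported positive PCR by Day 57 keep a sample that may be post-infection.

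About 7% to 10% of Day 57 PPI samples are affected under even spread, and roughly 5% to 15% once PCR detection and antibody lag are allowed to vary. With an assumed 3- to 10-fold rise, the Day 57 GMC is inflated by about 6% to 12% at 5% contamination and about 12% to 26% at 10%. If infection raises S-antibody at all, the bias in the GMC and in the fold rise from baseline is upward; its size rests on assumptions.

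The effect is confined to descriptive Day 57 summaries. It is worth correcting because the remedy is cheap and Day 57 carries the durability reading after one dose. It gives no reason to doubt the non-inferiority tests.

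**What to change.** Add to SAP 4.1, with a matching line in SAP 6.1.4: for participants who are N-negative at baseline and Day 29 and first N-positive at Day 71, the stored Day 57 serum is tested for N-antibody, and the Day 57 sample is excluded from the PPI if the result is positive.

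Add a sensitivity analysis of the Day 57 GMC, fold rise from baseline and responder rate that excludes the Day 57 samples of all such participants, whatever the Day 57 N-result. This also covers infections too recent for N-antibody to have appeared by Day 57. If the two sets of summaries agree, the question is closed.

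Cost: N-assays on a limited set of stored samples, already permitted by footnote l. At the main-study enrolment target this is about 11% × 1,350 = 149 samples, before dropout and PCR-known cases. The sensitivity analysis loses up to about 15% of Day 57 samples from Day 29 N-negatives, about a third of them probably pre-infection, which is why it should not be the main rule. No Day 29 or Day 71 data are lost.
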